1.3. Rationale

Malaria remains one of the most important infectious diseases worldwide with an estimated 3.3 billion people at risk leading to hundreds of millions of cases and 660,000 deaths each year.^{46, 76} In 2010, 81% of cases and 91% of deaths were estimated to have occurred in Africa, with children under five years of age and pregnant women most severely affected.⁴⁶ The primary tools currently available for malaria prevention in Africa include ITNs and IPTp. However, there are limitations with these interventions and the burden of malaria remains high in many parts of Africa despite recent increases in coverage levels. ITNs do not fully protect against malaria and there is concern for waning efficacy given the emergence of resistance to pyrethroid insecticides (the only class used in ITNs).^{32, 33} The only drug widely used for IPTp is SP, and there are recent reports suggesting that IPTp with SP is no longer effective, especially in East Africa, where resistance to this drug is now widespread.^{14, 77} Recent increases in funding for malaria control offer an unprecedented opportunity to expand preventative interventions; however, new strategies are urgently needed to reduce the burden of malaria for those at greatest risk.

One of the most important malaria control interventions is the use of ACTs for the treatment of malaria. ACTs are highly efficacious, and now the recommended first-line treatment for uncomplicated falciparum malaria in all countries of sub-Saharan Africa, including the treatment of malaria in pregnant women during the 2nd and 3rd trimesters.²⁵ ACTs also offer the opportunity to greatly reduce the burden of malaria in pregnant women and young children if their role is expanded to chemoprevention. IPT with the ACTs artesunate-amodiaquine, artesunate-SP, and DP have been shown to be effective and safe for the prevention of malaria in African children.^{41, 78, 79} IPT with DP is especially attractive given its

prolonged post-treatment prophylactic effect, due to the unusually long half-life of piperazine.²⁷

This proposal will be the first clinical trial we are aware of to evaluate the efficacy and safety of DP for the prevention of malaria in pregnant women. We will perform a randomized, double-blinded, controlled trial to compare 2 dosing strategies of this novel intervention with the current standard of care of IPTp with SP in an area of high transmission intensity and widespread antifolate resistance. Pregnant women will undergo frequent sampling using a highly sensitive PCR assay to better define the timing and frequency of malaria infection during pregnancy and the primary outcome will be based on placental histopathology to maximize the detection of placental infection throughout pregnancy. At enrollment mothers will also consent for participation of their unborn children in the 2nd phase of the study. Unborn children will be randomly assigned to receive q 3 monthly DP vs. monthly DP between 2-24 months of age and then followed for an additional 1 year after the intervention is stopped. We will be advancing the knowledge gained from our ongoing chemoprevention studies in infants by focusing on DP as the most effective candidate drug, utilizing a birth cohort and starting the intervention at an earlier age (2 months vs. 6 months) when the risk of malaria becomes high, and utilizing a double-blinded trial with directly observed therapy to more accurately assess safety and tolerability. In addition, by studying two different dosing strategies for DP in both pregnancy and infancy, we will be able to compare the practical benefits of less frequent dosing with the potential greater efficacy of more frequent dosing. Perhaps the most innovative and novel aspect of this proposal will be the use of a two-phase study design that will allow us to independently test the hypotheses that prevention of malaria in pregnancy and infancy will improve the acquisition of naturally acquired antimalarial immunity and reduce the subsequent risk of malaria in infants and young children. The overall theme of this proposal will be that in areas of high malaria transmission intensity where the burden of malaria remains high despite the use of currently available control interventions, aggressive and strategic use of highly effective drugs for chemoprevention may dramatically reduce malaria-associated morbidity and improve the development of antimalarial immunity.

2. STUDY OBJECTIVES

We will test the hypothesis that IPT with DP will significantly reduce the burden of malaria in pregnancy and infancy and improve the development of naturally acquired antimalarial immunity. The specific study objectives are as follows:

2.1. Objective 1

To compare the risk of placental malaria among HIV uninfected pregnant women randomized to receive IPTp with 3 dose SP vs. 3 dose DP vs. monthly DP. We will test the hypothesis that pregnant women who receive IPTp with either 3 doses of DP or monthly DP will have a lower risk of placental malaria defined by histopathology compared to those who receive 3 doses of SP. Secondary outcomes will include maternal and fetal clinical outcomes. We will also compare the two different dosing strategies of DP.

2.2. Objective 2

To compare the incidence of malaria among infants randomized to receive q 3 monthly DP vs. monthly DP between 2-24 months of age. We will test the hypothesis that infants randomized to receive monthly DP between 2-24 months of age will have a lower incidence of malaria during the first 24 months of life compared to infants randomized to receive q 3 monthly DP. Secondary outcomes will include the incidence of complicated malaria, hospitalizations, adverse events, and the prevalence of anemia.

2.3. Objective 3

To compare the incidence of malaria among infants and children following the two phases of the intervention. We will test the hypotheses that 1) infants born to mothers randomized to receive IPTp with 3 doses of DP or monthly DP will have a lower incidence of malaria during the first 24 months of life compared to infants born to mothers who were randomized to receive IPTp with 3 doses of SP, and 2) infants randomized to receive monthly DP between 2-24 months of age will have a lower incidence of malaria between 24-36 months of age after the intervention is stopped compared to infants randomized q 3 monthly DP between 2-24 months of age.

3. STUDY DESIGN

This will be a double-blinded randomized controlled phase III trial of 300 HIV uninfected pregnant women and the children born to them. The study interventions will be divided into two phases. In the first phase, HIV uninfected women at 12-20 weeks gestation will be randomized in equal proportions to one of three IPTp treatment arms: 1) 3 doses of SP, 2) 3 doses of DP, or 3) monthly DP. All three interventions arms will have either SP or DP placebo to ensure adequate blinding is achieved in the study as outlined in appendix D. Follow-up for the pregnant women will end approximately 6 weeks after giving birth. In the second phase of the study, all children born to mothers enrolled in the study will be followed from birth until they reach 36 months of age. Children born to mothers randomized to receive 3 doses of SP during

pregnancy will receive DP every 3 months between 2-24 months of age. Children born to mothers randomized to receive 3 doses of DP or monthly DP during pregnancy will receive either DP every 3 months or monthly DP between 2-24 months of age. To ensure adequate blinding, children who will receive DP every 3 months will be given DP placebo during the months they will not be taking DP. Children will then be followed an additional year between 24-36 months of age following the interventions.

4. SELECTION AND ENROLLMENT OF SUBJECTS

4.1. Inclusion Criteria

- 1) Pregnancy confirmed by positive urine pregnancy test or intrauterine pregnancy by ultrasound
- 2) Estimated gestational age between 12-20 weeks
- 3) Confirmed to be HIV uninfected by rapid test
- 4) 16 years of age or older
- 5) Residency within 30km of the study clinic
- 6) Provision of informed consent by the pregnant woman for herself and her unborn child
- 7) Agreement to come to the study clinic for any febrile episode or other illness and avoid medications given outside the study protocol
- 8) Plan to deliver in the hospital

4.2. Exclusion Criteria

- 1) History of serious adverse event to SP or DP
- 2) Active medical problem requiring inpatient evaluation at the time of screening
- 3) Intention of moving more than 30km from the study clinic
- 4) Chronic medical condition requiring frequent medical attention
- 5) Prior SP preventive therapy or any other antimalarial therapy during this pregnancy
- 6) Early or active labor (documented by cervical change with uterine contractions)

4.3. Initial Screening

We will recruit pregnant women presenting for routine care at the TDH antenatal clinic, at local health centers within 30 km, or referred by the Uganda government voluntary health teams. Pregnant women will be approached about participating in the study and will be provided an information sheet about the requirements of the study (Appendix A). If women are initially agreeable to screening for participation in the study and are ≤ 20 weeks gestation by LMP, 16 years of age or older, and not known to be HIV infected, they will either be escorted to the

study clinic or made an appointment to return at a later date. At our study clinic adjacent to the TDH antenatal clinic, study physicians will assess for initial eligibility criteria through conversation with the woman (confirming the age of the woman, residency within 30km of the study clinic, agreement to come to the study clinic for any febrile episode or other illness and avoid medications given outside the study protocol, plan to deliver in the hospital, no history of serious adverse event to SP or DP, no active medical problems requiring inpatient evaluation at the time of screening, no intention of moving more than 30km from the study clinic, no chronic medical condition requiring frequent medical attention, and no prior SP preventive therapy or any other antimalarial therapy during this pregnancy). Women who pass initial screening based on conversation with study physicians will undergo the following additional screening procedures: 1) rapid HIV testing to confirm HIV negative status, 2) ultrasound dating to confirm intrauterine pregnancy and gestational age of 12-20 weeks in conjunction with LMP (Appendix B), and 3) a pelvic examination to exclude early or active labor if clinically indicated. Women who are not eligible for the study will be referred back to the TDH antenatal clinic.

4.4. Study Enrollment Procedures and Baseline Evaluation

Informed consent will be obtained from women who pass initial screening. Study physicians will conduct the informed consent discussion in the study clinic. Informed consent will include both participation of the pregnant woman and her unborn child (or children in the case of non-singleton pregnancies). Informed consent will be conducted in the appropriate language and a translator will be used if necessary. The study will be described and consent obtained in one of 5 languages (Dopadhola, Ateso, Swahili, Luganda, or English). The consent forms will be translated into each language and back-translated into English to check for any loss or change of meaning. Following the informed consent discussion, pregnant women will be asked by the study physicians to sign a written consent form approved by the UCSF Committee for Human Research (UCSF CHR), Makerere University School of Medicine - Research and Ethics Committee (SOM-REC) or Makerere University School of Biomedical Sciences - Research and Ethics Committee (SBS-REC), and the Uganda National Council for Science and Technology (UNCST) for their own participation in the research study and a second approved consent form for the future use of biological specimens obtained during the course of the study. If the pregnant woman is unable to read or write, their fingerprint will substitute for a signature, and a signature from an impartial witness to the informed consent procedures will be obtained.

Women will be enrolled in study on the same day that they provide informed consent for participation in the research study. On the day of enrollment, women will undergo a standardized history and physical examination, and have blood collected by venipuncture (15 cc's) for filter paper sample (for future molecular studies), routine baseline laboratory testing and storage. Routine baseline laboratory testing will consist of a CBC and ALT measurement. Women who have history of fever in the previous 24 hours or a temperature $\geq 38.0^{\circ}\text{C}$ (tympanic) will have a thick blood smear read urgently in the study clinic. Women with history of fever in the previous 24 hours or a temperature $\geq 38.0^{\circ}\text{C}$ (tympanic) and a positive blood smear will be diagnosed with malaria and treated as described in section 6.2. At the end of the enrolment visit all study participants will be given a long lasting insecticide treated bed net

(ITN) and a household survey appointment will be scheduled within 2 weeks to collect household-level information on the use of bednets, house members, household characteristics, and GPS coordinates (Appendix C).

5. STUDY TREATMENT

5.1. Treatment Group Assignments

There will be 5 treatment arms which include both the intervention for the woman during pregnancy and her unborn child(ren) during infancy (Table 3). Non-singleton births from the same mother will be assigned to the same intervention. We will use a 2:1:1:1:1 randomization scheme targeting 100, 50, 50, 50, 50 pregnant women in treatment arms A-E respectively. A randomization list will be computer generated by a member of the project who will not be directly involved in the conduct of the study. The randomization list will include consecutive treatment numbers with corresponding random treatment assignments. Randomized codes will correspond to the 5 treatment groups using permuted variable sized blocks of 6 and 12 (to account for treatment group A being represented twice as often as the other 4 treatment groups). Sealed copies of the original randomization list and documentation of the procedure used to generate the lists will be stored in the project administrative offices in San Francisco and Kampala. Prior to the onset of the study, a set of sequentially numbered, opaque, sealed envelopes will be prepared. Each envelope will be marked on the outside with the treatment allocation number. The inside of the envelope will contain a piece of paper with the treatment allocation number and treatment group assignment along with a piece of carbon paper.

Table 3. Treatment arms with assignment of study drugs during pregnancy and infancy

Phase of intervention	Treatment arm				
	A	B	C	D	E
During pregnancy	3 dose SP	3 dose DP	3 dose DP	Monthly DP	Monthly DP
During infancy	3 monthly DP	3 monthly DP	Monthly DP	3 monthly DP	Monthly DP

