8.1.3. Analyses

An intention-to-treat approach to all analyses will be used, including all study participants randomized to therapy and including all follow-up time until the study participants complete the study or early study termination regardless of whether the intervention was stopped due to an adverse event.

Primary analysis. We will compare the prevalence of placental malaria defined by histopathology at birth between the study arms using the Chi-Square test for all pair-wise comparisons. We will explore for any differences of potential confounders between the treatment arms and if necessary adjust our analysis using multivariate logistic regression.

Secondary analyses. We will compare the prevalence of placental parasitemia and our composite birth outcome using the Chi-Square test. We will compare the incidence of maternal malaria and adverse events using Poisson or negative binomial regression models. The Poisson models will include the logarithm of the follow-up time as an offset. We will translate the fitted coefficients and their confidence bounds into percentage effects with the formula $100 * [\exp(\text{coefficient}) - 1]$. This approach is closely related to exponential survival models for analyzing events per follow-up time, but is better able to adjust for violated assumptions. Testing for overdispersion in the Poisson regression can detect violations of these assumptions, and variances can be adjusted accordingly to produce valid p-values and confidence interval. If significant deviations from required distributions in study data are detected, we will employ negative-binomial or zero-inflated negative-binomial models to account for the observed pattern of data. We will compare the prevalence of maternal anemia and asymptomatic parasitemia using generalized estimating equations with adjustments for repeated measures in the same study participant. If necessary, multivariate analyses will be performed to adjust for potential confounders and effect modifiers.

8.2. Hypothesis 2

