8.2.3. Analyses

An intention-to-treat approach to all analyses will be used, including all infants born to mothers assigned to receive IPTp with 3 dose DP or monthly DP and including all follow-up time until the

study participants reach 24 months of age or early study termination regardless of whether the intervention was stopped due to an adverse event.

Primary analysis. We will compare the incidence of malaria using Poisson or negative binomial regression models as described in section 9.1.3. In necessary, multivariate analyses will be performed to adjust for potential confounders and effect modifiers.

Secondary analyses. We will compare the incidence of complicated malaria, hospitalizations, and adverse events using Poisson or negative binomial regression models as described in section 9.1.3. We will compare the prevalence of anemia, asymptomatic parasitemia, and gametocytemia using generalized estimating equations with adjustments for repeated measures in the same study participant. In necessary, multivariate analyses will be performed to adjust for potential confounders and effect modifiers.

8.3. Hypothesis 3

We will test the hypotheses that A) infants born to mothers randomized to receive IPTp with 3 dose DP or monthly DP will have a lower incidence of malaria during the first 24 months of life compared to infants born to mothers who were randomized to receive IPTp with 3 doses of SP, and, B) infants randomized to receive monthly DP between 2-24 months of age will have a lower incidence of malaria between 24-36 months of age after the intervention is stopped compared to infants randomized q 3 monthly DP between 2-24 months of age. For hypothesis 3A, we will only include infants randomized to receive q 3 monthly DP during infancy. For hypothesis 3B, we will also explore for interaction with the intervention given during pregnancy.

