8.3.3. Analyses

An intention-to-treat approach to all analyses will be used. For hypothesis 3A, we will only include infants randomized to receive q 3 monthly DP during infancy. For hypothesis 3B, we will include all infants that reach 24 months of age. We will compare the incidence of malaria and the incidence of complicated malaria using Poisson or negative binomial regression models as described in section 9.1.3. For hypothesis 3B, we will also explore for interaction with the intervention given during pregnancy.

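### Siblings from multiple births always share one arm, but the infant analyses allow for no correlation between them, so standard errors are slightly too small if sibling outcomes are positively correlated

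*Protocol*

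**What the plan says.** Section 5.1 randomises women, using a "2:1:1:1:1 randomization scheme targeting 100, 50, 50, 50, 50 pregnant women in treatment arms A-E respectively". Consent under 4.4 covers the unborn child, "or children in the case of non-singleton pregnancies", and section 4.2 does not exclude multiple pregnancy. On allocation, section 5.1 states: "Non-singleton births from the same mother will be assigned to the same intervention".

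The infant analyses are then specified as follows.

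- Hypothesis 2 (8.2.3): "We will compare the incidence of malaria using Poisson or negative binomial regression models as described in section 9.1.3". The analysis set is every infant born to a mother in either DP arm of pregnancy. The cross-reference evidently means 8.1.3, because section 9.1 covers record keeping.
- Hypotheses 3A and 3B (8.3.3): "We will compare the incidence of malaria and the incidence of complicated malaria using Poisson or negative binomial regression models". For 3A the set is infants on 3-monthly DP; for 3B it is all infants who reach 24 months.
- Variance in the count models (8.1.3): after a test for overdispersion, "variances can be adjusted accordingly to produce valid p-values and confidence interval".
- Infant prevalence outcomes (8.2.3): "generalized estimating equations with adjustments for repeated measures in the same study participant".

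No analysis mentions siblings or the mother as a cluster. Table 9 plans 90 infants from 90 women per pregnancy arm, that is, one child per woman.

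**The concern.** The randomised unit is the mother, but the unit in the infant models is the child. The two differ only for multiple births, where the allocation rule puts all siblings in one arm. Siblings normally share a home and its mosquito exposure, and section 1.1 itself describes exposure as closely tied between mothers and their infants. Positive correlation between sibling malaria counts is therefore the natural expectation.

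Neither stated adjustment covers this. An overdispersion factor or a negative binomial variance describes extra variation between children; it still treats two children as independent. The GEE wording covers several measurements on one child, not measurements on two siblings. The stakes are confidence intervals that are somewhat too narrow for the primary outcomes of hypotheses 2, 3A and 3B, and for the infant secondary outcomes.

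**Working it through.** **1. The plan's own figure.** Table 10 gives a detectable difference of 18-23% for hypothesis 2 (90 v 90 infants, 3-5 episodes per person-year, two-sided alpha 0.05, power 80%). With independent children and SE(log rate ratio) = sqrt(1/E1 + 1/E2), take rate 3 and one person-year per child:

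- E1 = 90 × 3 = 270 and E2 = 270 × (1 − 0.2276) = 208.5.
- SE = sqrt(1/270 + 1/208.5) = 0.0922.
- 1 − exp(−(1.96 + 0.84) × 0.0922) = 22.8%.

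At rate 5 the result is 17.85%. The stated 23% and 18% are therefore reproduced under independence of children. They match at one person-year per child; about 1.9 years would give 16.8% and 13.1%. That does not affect the present point.

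**2. Inputs for the sibling effect.** The protocol gives neither the share of pregnancies that are twins (t) nor the ICC between siblings. Both are assumed: t = 1-5% and ICC = 0.1-0.5, with ICC = 1 as a bound. With 90 mothers in an arm, t = 1-5% means 0.9 to 4.5 twin pairs.

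**3. Formula.** From n mothers there are n(1 + t) children and nt pairs. Each pair adds 2 × ICC × σ² to the variance of the sum, so the design effect is

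DE = 1 + ICC × 2t / (1 + t).

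The SE is understated by 1 − 1/sqrt(DE), and the actual two-sided alpha is 2 × (1 − Φ(1.96/sqrt(DE))). Example for t = 5% and ICC = 0.5: DE = 1 + 0.5 × 0.10/1.05 = 1.0476, sqrt = 1.0235, 1.96/1.0235 = 1.915, alpha = 0.0555.

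| t | ICC | DE | SE understated | actual alpha |
|---|---|---|---|---|
| 1% | 0.1 | 1.0020 | 0.10% | 0.0502 |
| 1% | 0.5 | 1.0099 | 0.49% | 0.0511 |
| 2% | 0.5 | 1.0196 | 0.97% | 0.0523 |
| 3% | 0.5 | 1.0291 | 1.43% | 0.0534 |
| 5% | 0.1 | 1.0095 | 0.47% | 0.0511 |
| 5% | 0.5 | 1.0476 | 2.30% | 0.0555 |
| 5% | 1.0 (bound) | 1.0952 | 4.45% | 0.0611 |

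**4. Effect on the detectable difference.** With the number of children held at 90 per group, t = 5% and ICC = 0.5, the hypothesis 2 figures move from 22.76% to 23.27% (rate 3) and from 17.85% to 18.25% (rate 5). Power at the stated 23% falls from 80.9% to 79.0%.

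**5. Simulation check.** Setup: 90 mothers per arm, rate 3 over 1.9 years (mean 5.7), gamma frailty with variance 0.5 fully shared by twins, no treatment effect, 20,000 runs. Monte Carlo standard error is sqrt(0.05 × 0.95/20,000), about 0.15 points. Full sharing implies an ICC of 0.5 × 5.7/(1 + 0.5 × 5.7) = 0.74, which is above the main assumed range.

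| t | ignoring siblings | variance clustered on mother |
|---|---|---|
| 0 | 5.3% | 5.3% |
| 2% | 5.9% | 5.5% |
| 5% | 6.2% | 5.4% |

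This Wald test already rejects slightly more than 5% with no twins at all (5.3%, and 5.5% in a second no-twin run). Only the excess over that baseline, about 0.6 and 0.9 points against 5.3%, can be put down to twins. Clustering on the mother brings the rate back close to the baseline.

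**The case against.** The strongest reply is that a protocol usually names a model family and leaves the variance estimator to the statistical analysis plan, which is not shown. A cluster-robust variance would fit the wording of 8.2.3 and 8.3.3 without contradicting it, and nowhere does the protocol state that siblings are independent. That stands in part: this is an omission and not a contradiction. However, the protocol does more than name a family. It states the variance adjustment and the correlation structure to be handled, and its own allocation rule creates clusters that neither of them covers.

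The second reply is that the effect is negligible. On size this largely stands. A few twin pairs per 90 mothers cannot move standard errors by more than a few percent.

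A reader might also infer that the composite birth outcome is tested with every child counted as independent, because 8.1.3 says "We will compare the prevalence of placental parasitemia and our composite birth outcome using the Chi-Square test" and low birth weight and preterm delivery tend to be shared by twins. The protocol does not support that reading. It never names the child as the unit. The composite sits under hypothesis 1, which concerns pregnant women, and the analysis set there is the randomised participants. Counted once per pregnancy, the chi-square test has no clustering problem. All that can be said is that the unit is not stated.

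**Conclusion.** The point holds as a small one. Multiple pregnancies are eligible, siblings share an arm, and the infant models as written leave out correlation between siblings. If that correlation is positive, standard errors are understated by about 0.1-2.3% and type I error is about 5.0-5.6% in place of 5%, for assumed twin rates of 1-5% and ICC of 0.1-0.5. Even complete correlation at 5% twins gives 6.1%. These figures rest on assumptions, since the protocol supplies neither input.

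The documents do not support reading this as a threat to the primary conclusions. The detectable difference for hypothesis 2 moves by about half a percentage point or less. The hypothesis 1 primary outcome, placental malaria, is counted per woman in Table 9 and is unaffected on that basis. The change is worth making because it aligns the infant analysis with the randomised unit at almost no cost.

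**What to change.** In 8.2.3 and 8.3.3, state that every infant outcome is analysed with a robust variance clustered on the mother. In 8.2.3, make the mother the cluster in the infant GEE models, so that repeated measures on one child and measures on siblings fall in the same cluster. The cross-reference to 9.1.3 can be corrected to 8.1.3 in the same edit.

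For the composite birth outcome, 8.1.2 need at most confirm that the woman or pregnancy is the unit. If so, it should also say how a pregnancy with one affected and one unaffected sibling is scored. That rule is part of the outcome definition, so the investigators should choose it before unblinding.

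The cost is a few sentences and one option in the model call. Sample size, allocation and conduct do not change.
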